### **9.6.1 Primary Analysis**

Comparison between treatment arms of the primary endpoint will be undertaken using the Wilcoxon rank-sum test. The primary analysis will be as-treated, excluding participants who do not remain on the study regimen and/or participants who do not have an observed primary endpoint. Participants who discontinue study drug or their background entry regimen for  $\geq 14$  consecutive days will no longer contribute data to the primary outcome after the date on which they first discontinued medication. An intent-to-treat analysis will also be performed as a supplement.

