## **1.0 Study Hypotheses and Objectives**

### **1.1 Hypotheses**

1.1.1 Compared to continued ART, switch to bictegravir + tenofovir alafenamide + emtricitabine will not be associated with an adverse side effect profile and will maintain virologic control in HIV-infected transwomen (TW).

1.1.2 After 48 weeks, switch to bictegravir + tenofovir alafenamide + emtricitabine will be associated with improvements in circulating inflammatory and metabolic biomarker profiles (including mortality-associated biomarkers), bone mineral density, fat and lean mass quantities, hepatic fat and insulin resistance vs continued ART.

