## 9.3 Primary Endpoint Assessments

The safety (frequency of maintaining HIV-1 RNA <50 copies/mL) and tolerability (frequency of study drug discontinuation due to study-drug related AEs and frequency of study-drug related ≥ Grade 3 lab or clinical events whether or not study drug was discontinued) of bictegravir + tenofovir alafenamide + emtricitabine in HIV-infected TW on female hormone therapy vs continued ART.

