## **9.6 Analyses**

A descriptive analysis of demographic and clinical characteristics will be generated. Continuous variables will be expressed as mean  $\pm$  SD if normally distributed or median with IQR if not normally distributed. Data will be pooled by arm and stratified by ART 3rd drug class. CAP will be used continuously and categorically, using for the latter the following standardized steatosis cut-offs: Grade 1 238 dB/m, Grade 2 260 dB/m and Grade 3 292 dB/m. DXA data will be used continuously for lean and fat mass measurements, and, for bone mineral density, both continuously and categorically, with the latter using standard cutoffs for osteopenia and osteoporosis. Biomarker levels may be log-transformed, where appropriate. Wilcoxon rank-sum and Pearson  $\chi^2$  tests will compare continuous and categorical variables, respectively, between and within groups. Although the sample size is small, regression modeling will be attempted to assess if any observed differences persist after adjustment for confounding factors. All statistical tests will be 2-sided ( $\alpha=0.05$ ). Analysis will be exploratory without adjusting for multiple testing. [name] and [name] (statistician) will oversee analysis plan development/implementation.

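### Section 9.6.1 plans only a two-sided rank-sum test of the primary endpoint, with no between-arm estimate or interval, so a non-significant result would say little about whether virologic control is maintained

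*Combined protocol and SAP*

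**What the plan says.** Hypothesis 1.1.1 states that the switch, compared with continued ART, "will not be associated with an adverse side effect profile and will maintain virologic control". Section 9.3 makes this primary. Its safety part opens "The safety (frequency of maintaining HIV-1 RNA", with a threshold of 50 copies/mL. Its tolerability part is the "frequency of study drug discontinuation due to study-drug related AEs and frequency of study-drug related" events of grade 3 or higher.

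For the analysis, Section 9.6.1 says: "Comparison between treatment arms of the primary endpoint will be undertaken using the Wilcoxon rank-sum test". The primary set is as-treated, "excluding participants who do not remain on the study regimen and/or participants who do not have an observed primary endpoint". A further sentence says that people who stop for 14 days or more cease to contribute from the date they stopped. An intent-to-treat analysis is planned as a supplement.

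Section 9.6 adds general rules. Rank-sum and Pearson chi-square "tests will compare continuous and categorical variables, respectively, between and within groups". "All statistical tests will be 2-sided", at 0.05. "Analysis will be exploratory without adjusting for multiple testing". Regression is to be attempted, to see whether observed differences survive adjustment. Sections 9.6.2 and 9.6.3 report treatment-related AEs and treatment discontinuation by arm.

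Section 9.1 sizes the trial on FibroScan CAP: 20 evaluable and 24 enrolled per arm.

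**The concern.** The hypothesis is of the no-worse kind, but the planned method can only reject equality. Failing to reject is weak evidence of maintained control unless the study could have detected a loss that matters, and the sample size was not chosen for this endpoint. An interval would show how large a loss remains compatible with the data; the plan does not ask for one. At stake is how the primary result is reported: it could be a p-value carrying little information about the stated hypothesis.

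**Working it through.** **Inputs.** 20 evaluable and 24 enrolled per arm (Section 9.1); two-sided 0.05 (Section 9.6). The documents give no suppression rate on continued ART, so 95% is assumed, with a range of 90 to 100%. The natural reading of the safety endpoint is yes/no per participant, and the figures use it. Differences are switch minus continued ART.

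**The plan's own figure.** For CAP (difference 56 dB/m, SD 53, 90% power): n = 2 × (1.960 + 1.282)² × 53² / 56² = 18.8, so 19 per arm. A t-test with 20 per arm has power 0.90. The stated sample size reproduces, but it concerns a secondary endpoint.

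**One non-significant outcome.** On 0/1 data the tie-corrected rank-sum statistic squared equals Pearson chi-square × (N-1)/N. For 17/20 v 20/20:
- chi-square = 40 × (17×0 - 20×3)² / (20×20×37×3) = 3.243, p = 0.072
- rank-sum = 3.243 × 39/40 = 3.162, p = 0.075
- difference -15 points; Miettinen-Nurminen 95% CI -36.3 to +2.7 (Newcombe: -36.0 to +3.8)

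The planned output is a p-value of 0.075; the interval shows that a loss of about a third is not excluded.

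**Power of the planned test for a true 15-point loss** (sum of binomial probabilities over all outcomes with rank-sum p < 0.05):

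| Assumed rate on continued ART | 20 per arm | 24 per arm |
|---|---|---|
| 90% | 24% | 29% |
| 95% | 29% | 37% |
| 98% | 33% | 44% |
| 100% | 35% | 50% |

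**No failures in either arm.** All values tie, the rank-sum variance is zero and there is no p-value. If the true rate were 95% in both arms this would happen with probability 0.95^40 = 13% (20 per arm) or 0.95^48 = 9% (24 per arm). An interval still exists. With n/n in both arms, the Miettinen-Nurminen limit δ solves δ/(1-δ) = 3.84 × N / [n(N-1)]:
- 20 per arm: 3.84 × 40/(20×39) = 0.197, so δ = 16.5 points
- 24 per arm: 3.84 × 48/(24×47) = 0.163, so δ = 14.0 points

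**Analysis set (illustration).** Suppose 24 are randomised per arm and four in Arm A have confirmed failure. Section 8.1 lists this as a reason to stop study drug, and Section 6.4 takes such participants off study.
- If Section 9.6.1 excludes them: 20/20 v 24/24, difference 0, CI -16.4 to +14.1.
- If their data up to the stop still count as failures, or by intent-to-treat: 20/24 v 24/24, difference -16.7, CI -36.1 to -1.5, rank-sum p = 0.039.

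The text allows either reading, and the result depends on which is used.

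**The case against.** The best case for the plan is that this is a pilot, with analysis declared exploratory and no decision rule. A reader might infer that the investigators will declare control maintained whenever p exceeds 0.05. The documents do not say so. The primary objective is only to determine safety, and with about 24 per arm anyone given the counts can work out an interval. All of this stands, and it keeps the point modest. But exploratory status favours estimation over testing, and the plan does not require those counts for HIV-1 RNA: Sections 9.6.2 and 9.6.3 cover AEs and discontinuation. The regression in Section 9.6 names no effect measure or interval and is not assigned to this endpoint.

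The endpoint could instead be the share of the post-baseline HIV-1 RNA visits (weeks 4, 12, 24 and 48) at which a participant is suppressed. A rank-sum test would then fit, but an estimate and interval would still be missing.

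Three stronger readings are tempting and are not supported:
- *The rank-sum test is the wrong test and chi-square must replace it.* On yes/no data Section 9.6.1 does depart from the general rule in Section 9.6, but the two tests nearly coincide. The rank-sum agrees with the Miettinen-Nurminen statistic at zero difference, and Pearson can disagree with that interval: 17/20 v 24/24 gives Pearson p = 0.049, rank-sum p = 0.052 and an upper limit of +0.2.
- *The as-treated analysis necessarily loses the failures.* The sentence on contributing data until the stop can be read as keeping them, since failing values normally come before the stop.
- *Arm B has no related events by definition, so tolerability is biased.* Section 7.0 concerns toxicity management and Section 10.4 SAE reporting. Neither defines the endpoint, and Section 9.6.2 reports treatment-related AEs by arm.

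**Conclusion.** The point holds as a gap in planned reporting. The plan tests the primary endpoint without estimating the difference, and at this size the test cannot carry a statement that control is maintained. That the interval is missing follows from the text alone. The example interval and p-value depend only on the illustrative counts. The power of 29 to 37% assumes 95% maintained on continued ART; over assumed rates of 90 to 100% it runs from 24 to 50%. All these figures assume a yes/no endpoint.

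This is a low-cost improvement. A reader might infer that the trial needs a non-inferiority margin or more participants; nothing in a pilot with exploratory aims calls for either.

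**What to change.** In Section 9.6.1:
1. Define the HIV-1 RNA component as yes/no per participant at a stated time point. One option is below 50 copies/mL at week 48, with confirmed failure before then counted as not maintained, and a stated rule for other missing values.
2. Report the proportion per arm with an exact 95% CI, and the risk difference with a Miettinen-Nurminen 95% CI, in both the as-treated set and the intent-to-treat set already planned.
3. State that confirmed failures are kept as failures in the intent-to-treat set, and say which reading of the as-treated rule applies.
4. State that the conclusion on maintained control rests on the loss the interval excludes. The rank-sum p-value may stay.
5. For the two tolerability components, report per-arm proportions with exact 95% CIs. Give a between-arm difference only if relatedness is assessed in the same way in both arms.

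The cost is a few lines of text and trivial analysis, with no change to design, sample size or data collection, and no loss of power. The downside is a more modest conclusion: even a trial without a single failure would exclude only losses above about 14 points (24 per arm) to 16 points (20 per arm).

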## **8.0 Criteria For Discontinuation**

### **8.1 Permanent Study Drug Discontinuation**

Study drug discontinuation can occur for the following reasons:

- Drug-related toxicity requiring permanent discontinuation (see Section 7.1).
- Requirement for prohibited concomitant drugs (see section 5.4).
- Request by participant to terminate treatment.
- Confirmation of virologic failure (two measurements of HIV-1 RNA  $>200$  copies/mL at least 2 weeks apart).
- Clinical reasons believed life-threatening by the physician, even if not addressed in the toxicity section of the protocol.
- Participant repeatedly noncompliant with study drug as prescribed.
- Participant discontinues study drug for  $\geq 14$  consecutive days (Arm A).
- Participant discontinues background entry regimen for  $\geq 14$  consecutive days (Arm B).
- Failure by the participant to attend  $\geq 2$  consecutive study visits.

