### **8.3 Early Discontinuation**

Any participant who develops a Grade 3 or 4 symptom or laboratory abnormality (other than bilirubin, cholesterol and triglycerides, UNLESS THE INVESTIGATOR HAS A COMPELLING REASON TO THINK IT IS NOT RELATED TO STUDY DRUG) will be evaluated and will have study treatment withheld until the toxicity resolves ( $\leq$  Grade 2). If the abnormality is thought to be related to study treatment, the participant will not be rechallenged without discussion with [name] (see Section 7.2). Participants who have to discontinue study drug early (for the above listed reasons or confirmed virologic failure) but have been on study drug for at least 12 weeks will undergo a final safety evaluation, blood draw for stored serum and plasma, DXA scan and FibroScan. All participants will remain in follow-up for resolution of Grade 3 or 4 toxicities.

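### The as-treated exclusion in Section 9.6.1 removes events that the primary endpoint in Section 9.3 counts, and the sentence that would mostly repair this is not said to govern

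*Combined protocol and SAP*

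**What the plan says.** Safety is the only primary objective (Section 1.2). Section 9.3 gives the primary endpoint three parts: keeping HIV-1 RNA below 50 copies/mL; "frequency of study drug discontinuation due to study-drug related AEs"; and related Grade 3 or higher laboratory or clinical events, counted "whether or not study drug was discontinued".

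Section 9.6.1 then defines the analysis set in two consecutive sentences. The first reads "The primary analysis will be as-treated, excluding participants who do not remain on the study regimen" and also leaves out anyone without an observed primary endpoint. The second says that participants off study drug, or off the entry regimen, for 14 or more consecutive days "will no longer contribute data to the primary outcome after the date on which they first discontinued medication". The section adds: "An intent-to-treat analysis will also be performed as a supplement".

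Three other sections bear on who stops:

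- Section 8.1 opens with "Study drug discontinuation can occur for the following reasons" and lists confirmed virologic failure: two RNA values above 200 copies/mL at least 2 weeks apart.
- Section 8.3 treats confirmed failure as a case in which drug has to be stopped. For most Grade 3 or 4 abnormalities it says that participants "will have study treatment withheld until the toxicity resolves".
- Section 6.4 takes confirmed failures off study after a discontinuation visit.

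**The concern.** Someone who stops study drug for a related adverse event has, by that act, not remained on the regimen. If such people are excluded whole, the analysis set is selected on the outcome: it cannot contain one of the events it is meant to count. The same applies to a confirmed virologic failure who stops drug, whose removal raises the suppression rate that the failure should lower.

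Excluding a person and cutting a person's data at a date are different rules. The same data can therefore yield two primary safety results. The trial is open label, and under Section 9.5 the team regularly reviews adverse events and early stops by arm, so the choice between the rules could be made with outcomes in view.

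**Working it through.** **Plan's own figures.** The plan gives no expected rate for any part of the primary endpoint. Its fully specified sample-size calculation (Section 9.1) concerns CAP: difference 56, SD 53, d = 56/53 = 1.06. A two-sample t-test at two-sided 0.05 with 20 per arm has 90.2% power, matching the stated 90%. Only the 24 enrolled per arm and the 20% loss allowance (0.20 × 24 = 4.8 people) are used below.

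**The two sentences against the endpoint**

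| Event | Exclusion sentence, literal | Stop-date sentence |
|---|---|---|
| Stop for a related AE | Lost; zero by construction | Kept (falls on the stop date) |
| Related Grade 3+ event before the stop, in a stopper | Lost | Kept |
| Related Grade 3+ event after the stop | Lost | Lost |
| Failure confirmed before drug is stopped | Lost | Kept |
| First RNA >200 before the stop, confirmatory value after it | Lost | Confirmatory value lost |
| RNA 50–200, or any event, in someone who stays on drug | Kept | Kept |

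The third row conflicts with Section 9.3 under either sentence. The fifth can arise because the two RNA values must be at least 2 weeks apart.

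The plan also does not say whether a long treatment hold under Section 8.3 counts as not remaining on the regimen.

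**Illustration (all counts assumed).** Arm A has 24 participants: 2 failures confirmed before stopping drug, 2 related-AE stoppers with suppressed RNA up to the stop, and 20 others suppressed. The four stops are 4/24 = 16.7%, inside the 20% allowance. Intervals are exact (Clopper–Pearson) 95%.

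- Exclusion: suppression 20/20 = 100% (83.2–100); AE stops 0/20 = 0% (0–16.8).
- Stop-date, AE stoppers counted as suppressed: (20 + 2)/24 = 22/24 = 91.7% (73.0–99.0).
- Stop-date, AE stoppers out of the suppression denominator: 20/(24 − 2) = 20/22 = 90.9% (70.8–98.9).
- Stop-date, AE stops: 2/24 = 8.3% (1.0–27.0).

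The gap is 100 − 91.7 = 8.3 or 100 − 90.9 = 9.1 points of suppression, and 8.3 points of AE stops.

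**Other splits (failures + AE stoppers, of 24)**

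- 1 + 1: 23/24 or 22/23 suppressed; gap 4.2 to 4.3 points.
- 3 + 1: 21/24 or 20/23; gap 12.5 to 13.0 points.
- 4 + 0: 20/24; gap 16.7 points.
- 0 + 4: no suppression gap, but AE stops are 0/20 against 4/24 = 16.7%.

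**Tests against an assumed Arm B of 24/24 suppressed.** Wilcoxon is the test the plan names (here tie-corrected, no continuity correction).

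| Arm A, stop-date rule | Wilcoxon p | Fisher p |
|---|---|---|
| 22/24 | 0.15 | 0.49 |
| 20/22 | 0.14 | 0.22 |
| 20/24 (4 failures) | 0.039 | 0.11 |

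Under exclusion, Arm A is 20/20 in each of these cases and there is no difference to test.

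**The case against.** The best reply is that Section 9.6.1 reconciles itself. The stop-date sentence comes directly after the exclusion, covers both arms, and uses the 14-day threshold found in Sections 6.4 and 8.1. It would be redundant if stoppers had already been removed, because nobody can cease to contribute after a date when none of their data are used. This stands as the more natural reading. It does not close the point: the plan never says that the second sentence defines the first, and events after the stop are lost even so.

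Second, Sections 9.6.2 and 9.6.3 report treatment-related adverse events and discontinuations by arm with no exclusion, and an intent-to-treat analysis is planned. The events will therefore be visible. But those two sections are descriptive, 9.6.2 is not restricted to Grade 3+, and intent-to-treat is a supplement. None of them restores the events to the primary comparison.

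Third, the counts are invented, and Section 2.1 reports no bictegravir discontinuations for adverse events in Phase II. That is fair. If nobody stops for a related event and no failure stops drug, the two sentences agree on these components.

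Fourth, this is a pilot with exploratory analysis (Sections 2.1 and 9.6). Confirmed failures go immediately to the monitoring committee (Section 10.4), so participant oversight does not depend on 9.6.1. This stands, and it limits the severity.

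**Conclusion.** The conflict is real and follows from the text alone. Read literally, the exclusion removes related-AE discontinuations, related Grade 3+ events in stoppers, and confirmed failures who stop drug. The stop-date sentence repairs most of this but is not said to govern and is incomplete. In the 2 + 2 illustration the difference is 8 to 9 points of suppression and 8 points of AE stops. Those sizes rest wholly on assumed counts.

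A reader might infer four stronger things that the documents do not support:

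- **Every confirmed failure leaves the suppression rate.** Section 9.6.1 excludes those off the regimen or without an observed endpoint. Being taken off study is neither. The effect is most direct in Arm A; an Arm B failure who stays on the entry regimen with observed RNA is not clearly excluded.
- **The stop-date sentence counts everything.** It loses later related events and possibly a confirmatory RNA value.
- **The choice of sentence either never or always affects significance.** Neither holds. The 2 + 2 case is non-significant under both rules. With 4 failures the named Wilcoxon test gives 0.039, while Fisher gives 0.11.
- **The defect invalidates the trial or compels an as-randomised primary analysis.** It is a wording fault in an exploratory pilot that already plans intent-to-treat.

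The missing-RNA rule, the replaced non-starters and the meaning of drug-related in Arm B are separate matters and do not add to this point. Severity: should be fixed.

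**What to change.** In Section 9.6.1:

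1. Remove the whole-participant exclusion from the primary analysis.
2. Analyse related-AE discontinuation and related Grade 3+ events in all participants who start (Arm A) or continue (Arm B) their assigned regimen, including those who later stop, so that Section 9.3 is met as written.
3. For suppression, count confirmed virologic failure as not maintaining RNA below 50 copies/mL, even if drug is then stopped or the confirmatory value falls after the stop date. Apply the stop-date rule only to other discontinuations.
4. Keep the planned intent-to-treat analysis. Whether as-treated or as-randomised is labelled primary for suppression is the sponsor's choice, provided it is stated in advance.

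Separately, Section 6.4 keeps participants who stop for an adverse event on study, yet takes off study those who stop for 14 days or more, with no exemption for adverse-event stops. These statements must be reconciled; this point takes no view on which should apply.

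Cost: items 1 to 4 change wording only and add no visits. Reconciling Section 6.4 could alter what is collected after a stop. The downside is that reported suppression and tolerability may look slightly less favourable.

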### **9.6.2 Occurrence of Study-Related AE**

The number of participants who experience treatment-related AE from the first day of study treatment to Week 48 will be reported by arm.

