## **5.0 Study Treatment**

### **5.1 Regimens, Administration, and Duration**

Study treatment is open label bictegravir + tenofovir alafenamide + emtricitabine (only bictegravir is investigational).

At entry participants will be randomized 1:1 by the study team to:

ARM A (immediate switch): Switch current ART to bictegravir + tenofovir alafenamide + emtricitabine for 48 weeks

or

ARM B (no switch): Continue current therapy for 48 weeks

If randomized to ARM A at study entry, the subject will substitute bictegravir + tenofovir alafenamide + emtricitabine for their entry ART regimen.

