### Signs and Symptoms

At entry, record all signs and symptoms occurring in the 30 days prior to entry. After entry, record all signs and symptoms  $\geq$  Grade 2. This study will use the most current DAIDS toxicity grading system. Any signs or symptoms that lead to a change in the study drug, regardless of grade, must also be recorded.

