## **6.6. Laboratory Evaluations**

Fasting will be required for study entry and weeks 24 and 48. Fasting will be defined as nothing by mouth except water and medications for at least 8 hours prior to the lab draw. At screening and entry, all laboratory values, regardless of grade, must be recorded on the CRFs. For post-entry assessments, record all laboratory values for WBC, Hb, platelet, glucose, creatinine, AST, ALT, lipid profile, CD4+ T lymphocyte count and HIV-1 RNA, and any other  $\geq$  Grade 2 laboratory value. Any laboratory value leading to a change in ART treatment must be recorded regardless of grade. Fasting lab studies include: total cholesterol, LDL cholesterol, triglycerides, HDL cholesterol, glucose (at weeks 0, 24 or 48), insulin and all biomarker measurements.

The site must refer to the Division of AIDS Table for Grading the Severity of Adult and Pediatric Adverse Events (DAIDS AE Grading Table), Version 2.0, November 2014, which is available on site.

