## **7.0 Toxicity Management**

Criteria for participant management, dose interruptions, modifications, and discontinuation of drug treatment will be mandated only for toxicities attributable to study drug (for Arm A participants). Toxicities due to drugs in the background regimen/entry regimen (for Arm B participants) should be managed according to standard clinical practice, with the goal of maintaining continuous therapy, if possible.

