### **7.1. Grade 1 or 2 Toxicity**

Participants who develop a Grade 1 or 2 AE or toxicity may continue study drug.

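### Grade 1 symptoms that lead to an ART change must be recorded in Arm A but need not be in Arm B, and section 9.6.2 counts treatment-related AEs without stating which grades the data support

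*Combined protocol and SAP*

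**What the plan says.** **What is reported.** Section 9.6.2: "The number of participants who experience treatment-related AE from the first day of study treatment to Week 48 will be reported by arm". It names no grade. Section 7.1 shows that mild events count as AEs in this protocol: "Participants who develop a Grade 1 or 2 AE or toxicity may continue study drug".

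**What is recorded for symptoms.** Section 6.5 (Signs and Symptoms) has no grade limit for the period before entry: "At entry, record all signs and symptoms occurring in the 30 days prior to entry". For the period after entry it says "After entry, record all signs and symptoms" and continues with a threshold of Grade 2 or higher. There is one exception: "Any signs or symptoms that lead to a change in the study drug, regardless of grade, must also be recorded".

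**What is recorded for laboratory values and diagnoses.** Section 6.6 keeps all post-entry values of a named list (including WBC, haemoglobin, platelets, glucose, creatinine, AST, ALT and lipids) and other values from Grade 2. Its exception is worded more widely: "Any laboratory value leading to a change in ART treatment must be recorded regardless of grade". Section 6.5 (Diagnoses) keeps every confirmed or probable diagnosis, with no grade limit.

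**Whose drug is the study drug.** Section 5.1: "Study treatment is open label bictegravir + tenofovir alafenamide + emtricitabine (only bictegravir is investigational". Section 7.0 ties the term to one arm: "discontinuation of drug treatment will be mandated only for toxicities attributable to study drug (for Arm A participants". Sections 7.0 and 8.1 describe Arm B as having a background or entry regimen instead.

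**The concern.** The count in 9.6.2 and the recording rules in 6.5 and 6.6 do not fit together, in two ways.

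First, the lower-grade exception for symptoms depends on the arm. If a mild symptom makes a participant change ART, the rule requires it on the case report form in Arm A and is silent in Arm B. The laboratory exception has no such split.

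Second, the count mixes grade floors without saying so. Symptoms enter from Grade 2, listed laboratory values and diagnoses at any grade. A reader of the by-arm table would take it as all treatment-related AEs.

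Safety is the only primary objective (section 1.2), and the study goal names tolerability (section 2.1). Section 9.3 also compares discontinuation for drug-related AEs with continued ART, and the mild symptom behind a stop in Arm B need not be on record. It is reasonable to expect new mild symptoms more often in the arm that starts a new regimen, so even a common floor could hide a difference. That is an inference, because the documents give no rates.

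**Working it through.** The plan states no figure on this point, so there is none to reproduce. The check is a comparison of the rules, followed by an illustration of size.

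**Step 1. What must be recorded after entry, by arm**

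| Event | Arm A | Arm B | Source |
|---|---|---|---|
| Symptom, Grade 2 or higher | yes | yes | 6.5 |
| Symptom, Grade 1, no drug change | no | no | 6.5 |
| Symptom, Grade 1, leads to ART change | **yes** | **not required** | 6.5 with 5.1, 7.0, 8.1 |
| Listed laboratory value, Grade 1 | yes | yes | 6.6 |
| Other laboratory value, Grade 1, no ART change | no | no | 6.6 |
| Other laboratory value, Grade 1, leads to ART change | yes | yes | 6.6 |
| Diagnosis, any grade | yes | yes | 6.5 |
| The ART change itself | yes | yes | 6.5 |

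Only the third row differs between arms. The last row does not repair it: the ART modification is recorded in Arm B, but nothing requires the Grade 1 symptom that caused it. Section 9.6.3 lists reasons for stopping, but again for study drug.

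**Step 2. Effect on the 9.6.2 count**

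Set against the table, an ungraded count of treatment-related AEs takes in rows 1, 4, 6 and 7 in both arms, row 3 in Arm A only, and rows 2 and 5 in neither.

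**Step 3. Illustration of size**

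Inputs:
- n = 24 per arm (section 9.1).
- g = share of an arm whose only related AE is a Grade 1 symptom. Assumed, 5% to 30%, the same in both arms.
- c = share of those whose symptom leads to a drug change. Assumed, 0% to 20%.

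Sites are taken to record only what the rules require. Expected participants uncounted are n × g in Arm B and n × g × (1 − c) in Arm A. The gap is n × g × c.

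| g | c | Arm B uncounted | Arm A uncounted | Gap |
|---|---|---|---|---|
| 5% | 0% | 24 × 0.05 = 1.2 | 1.2 | 0 |
| 5% | 20% | 1.2 | 1.2 × 0.80 = 0.96 | 0.24 |
| 10% | 10% | 24 × 0.10 = 2.4 | 2.4 × 0.90 = 2.16 | 0.24 |
| 30% | 0% | 24 × 0.30 = 7.2 | 7.2 | 0 |
| 30% | 20% | 7.2 | 7.2 × 0.80 = 5.76 | 1.44 |

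Over this range 1.2 to 7.2 participants go uncounted in Arm B, and the gap due to the exception is 0 to 1.4.

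**The case against.** The Grade 2 floor is a deliberate and legitimate choice. The monthly summary in section 9.5 uses the same floor for signs and symptoms, and 9.5 then speaks of a quarterly report of all AEs, so the protocol may simply use AE for whatever it records. On that reading 9.6.2 lacks only a footnote. The count is descriptive, carries no test, and section 9.6 declares the analysis exploratory. Arm B enters on ART unchanged for at least 12 weeks before screening, so symptom-driven changes there are plausibly few. This limits the size of the problem, and it stands as far as that. It does not explain why the symptom exception is tied to one arm while the laboratory exception is not, and section 7.1 uses AE for Grade 1 events.

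A further objection is that the arms would not be comparable even with the exception reworded. Section 5.1 defines study treatment as the switch regimen only, so neither relatedness nor the first day of treatment has a stated meaning in Arm B. This is right, and the fix has to cover it.

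A reader might infer that mild events are missing altogether, or that the count cannot be produced. The documents do not support that: listed laboratory values are kept at every grade, all diagnoses are kept, and in Arm A symptoms that change the study drug are kept.

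**Conclusion.** The point holds in a limited form. The symptom exception in 6.5 ascertains Grade 1 events differently by arm, and 9.6.2 reports a count with unlabelled, mixed grade floors. The first is a defect in a stated rule. The second is mainly a matter of labelling.

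The effect is confined to Grade 1 events. Under the assumed rates the difference between arms is at most about 1.4 participants of 24, so it is real in wording and probably small. The shared omission could be larger, but its size rests entirely on assumption.

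A reader might go further and infer that the true any-grade rate is several times the reported one. No Grade 1 rate in the documents supports this, and such a contrast would also have to treat the recorded Grade 1 laboratory values and diagnoses as lost. A reader might also infer that the primary tolerability result is undermined. Events of Grade 3 or higher lie above the floor in both arms. Only the discontinuation component is touched, and only through the missing record of a mild symptom behind an Arm B change.

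**What to change.** 1. **Section 6.5, Signs and Symptoms:** extend the any-grade exception to symptoms that lead to a change in study drug or in entry ART, to match 6.6.
2. **Section 9.6.2:** report by arm the participants with treatment-related AEs of Grade 2 or higher. In a separate row, report those with treatment-related AEs of any grade that led to an ART change, in either arm.
3. **Section 9.6.2, Arm B:** state that treatment means the entry ART regimen, counted from the baseline visit.

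The cost is wording in two sections and a few extra symptom entries in Arm B. The downside is that the count becomes narrower than AEs of all grades, and its main row leaves out Grade 1 laboratory values and diagnoses that are recorded.
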